**Fluid Management:**

Total Intake since randomization:  mL

Total Output since randomization (include dialysis/CRRT):  mL

Plasma sample collected:  Yes     No

Blood collected: / /   Processed: / /    
MONTH D D Y Y Y Y TIME (0-2400) MONTH D D Y Y Y Y TIME (0-2400)

Number 0.5 ml aliquots:  1     2     3     4     5     6     7     8     9     10

Date/Time placed in -80°C freezer: / /    
MONTH D D Y Y Y Y TIME (0-2400)

Location in freezer: \_\_\_\_\_    Temperature reading on freezer: \_\_\_\_\_ °C

SITE ID		PATIENT ID			LETTER CODE		

## DAILY DATA – Day 04

(to be obtained as close to 0800 as possible on day 2 after randomization)

Form Completed by \_\_\_\_\_

MONTH			D D		Y Y Y Y			TIME (0-2400)	

Vital status  Alive  Dead

If Dead Date/Time of death:

MONTH			D D		Y Y Y Y			TIME (0-2400)	

Cause of death (from discharge summary/discussion with ICU team), then skip to question 11.

- Respiratory failure  
  Cardiac (arrhythmia, ACS, cardiogenic shock)  
  Multi-organ failure  
 Refractory shock  
  Intraabdominal (perforation, compartment)  
  Withdrawal of care  
 Neurological devastation  
  Severe sepsis  
  Refractory acidosis  
  Hemorrhage

Still receiving NMB?  Yes  No

If No and discontinued in last 24 hrs, answer following questions:

Date/Time discontinued:

MONTH			D D		Y Y Y Y			TIME (0-2400)	

Reason for discontinuation:  Refractory bradycardia  
 Possible drug reaction  
 Decision of ICU provider  
 Decision of family.  
 As per Study protocol

Date/Time: neuromuscular function (4 twitches/TOF) returned:

MONTH			D D		Y Y Y Y			TIME (0-2400)	

or  Did not return

Is patient in hypothermia group?  Yes  No **If “No” skip to question 13**

Did patient complete 48 hours of cooling?  Yes  No **If “Yes” skip to question 14**

If No, when was cooling stopped?

MONTH			D D		Y Y Y Y			TIME (0-2400)	

Reason for discontinuation:  Refractory bradycardia with hypotension  
 Hemorrhage  
 Intractable ventricular arrhythmia  
 Decision of ICU provider  
 Decision of family

**Skip to question 14.**

If in the Control arm, received therapeutic hypothermia in last 24 hrs?  Yes  No  N/A

Still intubated or receiving Assisted Breathing?  Yes  No  N/A

If No, when was patient extubated or UAB for ≥48 hours?

MONTH			D D		Y Y Y Y			TIME (0-2400)	

Was RRT started in last 24 hrs?  Yes  No  N/A

If RRT had been previously initiated has it stopped since randomization?  Yes  No  N/A

In the last 24 hrs did the patient have any of the following:

- Bradycardia (with mean arterial pressure < 65 mm Hg or needing pressors)  Yes  No  
 Significant Bleeding (Required IR, Surgery or >3u pRBCs)  Yes  No  
 Diagnosis of new pneumonia  Yes  No

**Vital signs in last 24 hrs**

Systolic BP: Lowest:    Highest:    mm Hg      Single

Diastolic BP: Lowest:    Highest:    mm Hg      Single

CVP: Lowest:   Highest:   cm H2O    CVP not available     Single

Mean arterial pressure: Lowest:    Highest:    mm Hg      Single

--	--	--	--	--	--	--	--

SITE ID    PATIENT ID    LETTER CODE

For each 2 hr block for the last 24 hrs record highest and lowest temperature and lowest SpO2 and the FiO2 and Mean Airway Pressure measured closest to the SpO2 reading. If only single temperature measurement for block, check "Single value" box. If no SpO2 measured for block, check the "None" box.

Time period	Temp (°C) If only one value record as "Low" and check box	Site of Temp measurement	Low SpO 2 (%) *	FiO 2 (%)	Mean airway pressure (cm H 2 O)
0801 to 1000	High:	 Esophageal  Urinary	None 		
	Low: 	 Peripheral  IV			
1001 to 1200	High:	 Esophageal  Urinary	None 		
	Low: 	 Peripheral  IV			
1201 to 1400	High:	 Esophageal  Urinary	None 		
	Low: 	 Peripheral  IV			
1401 to 1600	High:	 Esophageal  Urinary	None 		
	Low: 	 Peripheral  IV			
1601 to 1800	High:	 Esophageal  Urinary	None 		
	Low: 	 Peripheral  IV			
1801 to 2000	High:	 Esophageal  Urinary	None 		
	Low: 	 Peripheral  IV			
2001 to 2200	High:	 Esophageal  Urinary	None 		
	Low: 	 Peripheral  IV			
2201 to 2400	High:	 Esophageal  Urinary	None 		
	Low: 	 Peripheral  IV			
0001 to 0200	High:	 Esophageal  Urinary	None 		
	Low: 	 Peripheral  IV			
0201 to 0400	High:	 Esophageal  Urinary	None 		
	Low: 	 Peripheral  IV			
0401 to 0600	High:	 Esophageal  Urinary	None 		
	Low: 	 Peripheral  IV			
0601- to 0800	High:	 Esophageal  Urinary	None 		
	Low: 	 Peripheral  IV			

**In last 24 hours did patient receive?**

**Corticosteroid:** Yes No If yes, total daily dose (prednisone equivalent):    mg  
 1 mg prednisone/methylprednisolone = 4 mg hydrocortisone; 1 mg dexamethasone = 25 mg hydrocortisone

**Inhaled vasodilator:** Yes No If "Yes": indicate agent(s) used and total hrs administered  
Epoprostenol Nitric Oxide Total hours administered:

SITE ID		PATIENT ID				LETTER CODE			

**Vasopressor support in last 24 hrs** Yes No **If No proceed to question 23.**  
**(check all received and highest infusion rate for each):**

- Dobutamine   .   µg/kg/min OR µg/min
- Dopamine   .   µg/kg/min OR µg/min
- Norepinephrine   .   µg/kg/min OR µg/min
- Epinephrine   .   µg/kg/min OR µg/min
- Vasopressin   .   units/min
- Phenylephrine   .   µg/kg/min OR µg/min
- Milrinone   .   µg/kg/min OR µg/min

Total hours receiving vasopressor support:

Did the patient start proning Yes No or stop proning Yes No in the last 24 hours?

**Laboratory data (if only one value, record in "Lowest" field and click "Single" box; if no data, click "None" box):**

**CBC values:**

- WBC: Lowest:    Highest:    x1000/mm^3 Single  None
- Hgb: Lowest:    Highest:   g/dL Single  None
- Hct: Lowest:    Highest:   % Single  None
- Platelets: Lowest:    x1000/mm^3 None

**Serum Levels:**

- Potassium: Lowest:  .  Highest:  .  mEq/L Single  None
- Bicarbonate: Lowest:   .  Highest:   .  mEq/dL Single  None
- BUN: Lowest:   .  Highest:   .  mg/dL Single  None
- Creatinine: Lowest:    Highest:    mg/dL Single  None
- Glucose: Lowest:    Highest:    mg/dL Single  None
- Magnesium: Lowest:  .  Highest:  .  mmol/L Single  None
- Phosphate: Lowest:  .  Highest:  .  mg/dL Single  None
- Albumin: Lowest:  .  Highest:  .  g/dL Single  None
- Bilirubin: Lowest:   .  Highest:   .  mg/dL Single  None
- Highest AST:     U/L None  Highest ALT:     U/L None

**Highest/Lowest finger stick glucose every 6 hrs for last 24 hrs (if only single value, enter in**

Time Period	Lowest Glucose (mg/dL)	Date	Time	Highest Glucose	Date	Time	Single value	None
0601-1200								
1201-1800								
1801-2400								
0001-600								

**"Lowest" field and check "Single value" box; If no data, check "None" box:**

SITE ID		PATIENT ID				LETTER CODE			

If patient was extubated/UAB >24 hours ago, go to question 34

Ventilator mode/parameters used in last 24 hrs (check all that apply, circle the current one)

 DRAEGER	 SERVO
 PC-CMV  VC-CMV  SPN-CPAP/PS	 VC-AC  BiVent
 PC-AC  VC-AC  SPN-CPAP/VS	 PC-AC  PS
 PC-SIMV  VC-SIMV  SPN-PPS	 PRVC  VS
 PC-BIPAP  VC-MMV  SPN-CPAP	 VC-SIMV  CPAP
 PC-APRV	 PC-SIMV  NIV
 PC-HFO	 PRVC-SIMV
 PC-MMV	
 Other _____	

Extubated:  Yes  No    If Yes, Date/Time of extubation: / /   TIME (0-2400)

**ARDSNet Ventilation Adherence Data (if still intubated and mechanically ventilated):**

Measured Tidal Volumes:    Lowest:  ml    Highest:  ml

Estimated hours patient ventilated with tidal volume > 7 ml/kg     .  hrs

Applied PEEP:    Lowest:  cm H2O    Highest:  cm H2O

Mean airway pressure:    Lowest:  cm H2O    Highest:  cm H2O

**Lung Physiology Parameters (recorded 0600 to 1000 day 2 post-randomization; If no data available, check "No values" box. If patient not intubated, check "Not intubated" box)**

Plateau Pressure: cm H2O and associated PEEP:  cm H2O.  
 No values:     Not intubated:

**Arterial Blood Gas (if only one value, record in "Lowest" field and check "Single value" box. If no ABG data check "None" box)**

PaO2 /FiO2:    Lowest:  mm Hg/ %    Highest:  mm Hg/ % mm Hg  
 Single Value:     None:

**Fluid Management:**

Total Intake since randomization:  mL

Total Output since randomization (include dialysis/CRRT):  mL

Plasma sample collected:  Yes     No

Blood collected: / /   TIME (0-2400)    Processed: / /   TIME (0-2400)

Number 0.5 ml aliquots:  1     2     3     4     5     6     7     8     9     10

Date/Time placed in -80°C freezer: / /   TIME (0-2400)

Location in freezer: \_\_\_\_\_    Temperature reading on freezer: \_\_\_\_\_ °C

SITE ID		PATIENT ID			LETTER CODE		

## DAILY DATA – Day 07

(to be obtained as close to 0800 as possible day 7 after randomization)

Form Completed by \_\_\_\_\_

MONTH			D	D	Y	Y	TIME (0-		

Vital status  Alive  Dead

If Dead Date/Time of death:

MONTH			D	D	Y	Y	Y	Y	TIME (0-2400)

Cause of death (from discharge summary/discussion with ICU team), then skip to question 11.

- Respiratory failure  
  Cardiac (arrhythmia, ACS, cardiogenic shock)  
  Multi-organ failure  
 Refractory shock  
  Intraabdominal (perforation, compartment)  
  Withdrawal of care  
 Neurological devastation  
  Severe sepsis  
  Refractory acidosis  
  Hemorrhage

Still receiving NMB?  Yes  No

If No and discontinued in last 24 hrs, answer following questions:

Date/Time discontinued:

MONTH			D	D	Y	Y	Y	Y	TIME (0-2400)

Reason for discontinuation:  Refractory bradycardia  Possible drug reaction

- Decision of ICU provider  
  Decision of family

Date/Time: neuromuscular function (4 twitches/TOF) returned:

MONTH			D	D	Y	Y	Y	Y	TIME (0-2400)

or  Did not return

Did the patient receive therapeutic hypothermia in last 72 hrs?  Yes  No

If "Yes" how for many hours  and to what temperature (lowest)?  °C

Still intubated or receiving Assisted Breathing?  Yes  No  N/A

If No, when was patient extubated?

MONTH			D	D	Y	Y	Y	Y	TIME (0-2400)

Was RRT started in last 24 hrs?  Yes  No  N/A

If RRT had been previously initiated has it stopped since randomization?  Yes  No  N/A

In the last 24 hrs did the patient have any of the following:

- Bradycardia (with mean arterial pressure < 65 mm Hg or needing pressors)  Yes  No  
 Significant Bleeding (Required IR, Surgery or >3u pRBCs)  Yes  No  
 Diagnosis of new pneumonia  Yes  No

Vital signs in last 24 hrs

Systolic BP: Lowest:  Highest:  mm Hg Single

Diastolic BP: Lowest:  Highest:  mm Hg Single

CVP: Lowest:  Highest:  cm H2O CVP not available  Single

Mean arterial pressure: Lowest:  Highest:  mm Hg Single

--	--	--	--	--	--	--	--

SITE ID PATIENT ID LETTER CODE

For each 6 hr block for the last 72 hrs record the lowest SpO2 and the FiO2 and Mean Airway Pressure measured closest to the SpO2 reading. If no SpO2 measured for block, check the "None" box.

Time Period	Date	Time	SpO 2 (pulse Ox) (%)	FiO 2 (%)	Mean airway pressure (cm H 2 O)
Day 4 after Randomization					
0600-1200					
1200-1800					
1800-2400					
Day 5 after Randomization					
00-600					
0600-1200					
1200-1800					
1800-2400					
Day 6 after Randomization					
00-600					
0600-1200					
1200-1800					
1800-2400					
Day 7 after Randomization					
00-600					

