#### 10.7/ Day 7 Data CRF

- Record site ID code, 3-digit study ID, and the unique 3 letter identifier in the indicated fields at the top of the worksheet.
- Record your name and the date and time CRF was completed in the indicated fields on line 1.
- Indicate if still alive by checking appropriate “Yes/No” box on line 2 and, if “No,” record date and time of death in the indicated fields on line 3 and check the box next to the most appropriate cause of death (based on information from the discharge summary and discussion with the ICU provider team) on line 4.
- Indicate whether patient is still receiving NMB by checking appropriate “Yes/No” box on line 5 and, if “No,” record date and time it was discontinued on line 6, check the appropriate box for the major reason it was discontinued on line 7 (only check one box), and record the time neuromuscular function return (based on return of 4 twitches on train of 4 testing) in the indicated fields on line 8 or check the “no” box if neuromuscular function did not return through day 7.
- Indicate whether patient (regardless of treatment arm) received therapeutic hypothermia (intentional cooling to core temperature <36°C) in the last 72 hours (study days 5-7) by checking the appropriate Yes/No box on line 9 and enter the total time cooled and the lowest core temperature in the indicated fields.
- Indicate whether patient is still intubated (or if the patient has a tracheostomy, whether they are still receiving continuous mechanical ventilation (with <24h interruption) by checking appropriate yes/no box on line 10 and if “No” record date and time patient was extubated or was UAB for ≥48h in the indicated fields.
- Indicate whether patient was started on renal replacement therapy (RRT) in the past 24 hours by checking appropriate “Yes/No” box on line 11. If the patient was already receiving RRT, check the N/A box.

- If the patient was already receiving RRT, indicate whether it was discontinued in the past 24 hours by checking appropriate “Yes/No” box on line 12. If the patient was not previously receiving RRT, check the N/A box.
- On line 13, please indicate if any of the adverse events occurred in the last 24 hours by checking the appropriate “Yes/No” boxes.

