## 11./ Study Associated Risks and Risk Mitigation

a./ Although not expected to occur with modest TH to 34°-35°C, patients can develop:

b./ (1) persistent severe bradycardia (heart rate <30 associated with mean arterial pressure <65 without vasopressors); (2) uncontrolled bleeding and (3) intractable ventricular arrhythmias, there. In the event any of these conditions happens, TH protocol will be early terminated following clinical guidelines.

(4)There is a slightly Increased risk of infection, study subjects are closely monitored for infection and the appropriate use of antibiotics should be initiated as standard of care; (5) there is a mild risk of changes in fluid and chemical balance, this patient population is closely monitored and correction is implemented as standard of care; (5) there is a mild to moderate risk of hyperglycemia occur, this patient population is closely monitored and correction should be implemented as standard of care; (6) there is a slight reduction in the ability of blood clotting mechanism, this patient population is closely monitored and corrections should be implemented as standard of care.

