**eTable 2: Imputed PF ratio (cells) for combinations of SpO2 (rows) and FiO2 (columns)**

	0.30	0.35	0.40	0.45	0.50	0.55	0.60	0.65	0.70	0.75	0.80	0.85	0.90	0.95	1.00
80%	148	127	111	98	89	81	74	68	63	59	55	52	49	47	44
81%	151	129	113	101	91	82	76	70	65	60	57	53	50	48	45
82%	155	132	116	103	93	84	77	71	66	62	58	55	52	49	46
83%	158	136	119	106	95	86	79	73	68	63	59	56	53	50	47
84%	162	139	122	108	97	89	81	75	70	65	61	57	54	51	49
85%	167	143	125	111	100	91	83	77	71	67	63	59	56	53	50
86%	171	147	129	114	103	94	86	79	73	69	64	61	57	54	51
87%	177	151	132	118	106	96	88	81	76	71	66	62	59	56	53
88%	182	156	137	121	109	99	91	84	78	73	68	64	61	58	55
89%	189	162	141	126	113	103	94	87	81	75	71	67	63	60	57
90%	196	168	147	130	117	107	98	90	84	78	73	69	65	62	59
91%	203	174	153	136	122	111	102	94	87	81	76	72	68	64	61
92%	213	182	159	142	128	116	106	98	91	85	80	75	71	67	64
93%	223	191	168	149	134	122	112	103	96	89	84	79	74	71	67
94%	236	202	177	157	142	129	118	109	101	94	89	83	79	75	71
95%	252	216	189	168	151	138	126	116	108	101	95	89	84	80	76
96%	273	234	205	182	164	149	136	126	117	109	102	96	91	86	82

Conditions required to use inferred P/F ratio include: (a) SpO2 values 80-96%, (b) SpO2 measured ≥10 min after FiO2 change, (c) PEEP ≥ 8 cm H2O, (d) adequate pulse oximeter wave form, and (e) qualifying inferred P/F ratio is confirmed 1-6 hrs after the initial determination.

P/F ratio criterion met within 7 ventilator days

- Yes Collect **baseline blood sample**, randomize and record randomization time and treatment assignment below
- No STOP

Is this patient currently receiving prone positioning alternating with supine positioning?

- Yes
- No

Randomization date/time:    /   /          
MONTH D D Y Y Y Y TIME (0-2400)

Treatment assignment (check one)

- Therapeutic Hypothermia
- Usual Treatment

Initiate sedation, NMB, and cooling protocol for subjects randomized to Therapeutic Hypothermia

Complete Baseline information CRF.

See schedule for first week blood and data collection below.

--	--

[figure not shown]
SITE ID

--	--	--	--

PATIENT ID

--	--	--

LETTER CODE

- Collect baseline blood and complete Baseline CRF based on 24h preceding randomization
- Collect day 1 blood and complete Day 1 CRF at 0800 on randomization day + 1; (the duration of day 1 may be 8h 1 min to 31h 59 min as indicated by the examples a - c)

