- Collect blood and complete CRFs for Day 2, 3, 4, and 7 at 0800 on randomization day + 2, +3, +4, and +7 covering the prior 24h period

SITE ID		PATIENT ID				LETTER CODE			

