**(check all received and highest infusion rate for each):**

- Dobutamine   .   µg/kg/min OR µg/min
- Dopamine   .   µg/kg/min OR µg/min
- Norepinephrine   .   µg/kg/min OR µg/min
- Epinephrine   .   µg/kg/min OR µg/min
- Vasopressin   .   units/min
- Phenylephrine   .   µg/kg/min OR µg/min
- Milrinone   .   µg/kg/min OR µg/min

Total hours receiving vasopressor support:

Did the patient start proning Yes No or stop proning Yes No in the last 72 hours?

SITE ID		PATIENT ID				LETTER CODE			

 **Laboratory data (if only one value, record in “Lowest” field and click “Single” box; if no data, click “None” box):**

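### Day 7 form line 13 looks back only 24 h, so no event-specific prompt for bradycardia, significant bleeding or new pneumonia covers the 48 h from Day 4 0800 to Day 6 0800

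*Protocol*

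**What the plan says.** **Prompted safety events.** The daily forms in the Protocol appendix carry yes/no boxes for three events: bradycardia with low arterial pressure or pressor need, significant bleeding, and a new diagnosis of pneumonia. The Day 1 form covers the time since randomization. Section 10.5 (Days 2 and 3) and the Day 4 form each cover 24 h.

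**Day 7.** Line 13 of the form (Appendix, Daily Data – Day 07) asks "In the last 24 hrs did the patient have any of the following". The instruction in Section 10.7 matches: "On line 13, please indicate if any of the adverse events occurred in the last 24 hours". The collection schedule at the end of the Screening/Enrollment/Randomization source document describes the Day 2, 3, 4 and 7 forms as "covering the prior 24h period", each ending at 0800. The appendix list of forms goes from Day 4 straight to Day 7.

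**Other lines on the Day 7 form.** Line 9 (therapeutic hypothermia), line 15 (oxygenation table) and line 19 (proning, "in the last 72 hours") look back 72 h.

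**Other safety capture.** Section 2.2.3.2 makes site staff responsible for recording all AEs on a CRF. The Adverse Event CRF asks one general question, then takes dated free-text entries with no look-back limit. Section 3.5 has study personnel seeing patients daily for the first 7 days.

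**How safety is judged.** Section 1.1 puts safety measures in the primary outcome. Aim 1 (Section 1.2) refers to serious adverse effects compared with control. The SAP's one named safety analysis is a chi-square test on SAEs.

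**The concern.** The Day 4 boxes close at 0800 on Day 4 and the Day 7 boxes open at 0800 on Day 6. A coordinator who answers literally ticks No on Day 7 for a pneumonia diagnosed, or a bleed that occurred, on Day 5. Nothing else on the daily forms asks about it.

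The window matters because of where it falls. Section 11 lists risks of hypothermia that include "There is a slightly Increased risk of infection" and reduced clotting. A pneumonia acquired during cooling and paralysis may be diagnosed in the days that follow. Safety is a main reason for the pilot, and with 20 patients a difference of one or two events could change how the result reads. If the by-arm safety picture is drawn from the checkboxes, events in this window will not be in it.

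**Working it through.** The plan states no figure for this point, so there is none to reproduce. The check is interval arithmetic on the form windows.

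**Inputs**
- Length of Day 1, L: "the duration of day 1 may be 8h 1 min to 31h 59 min" (collection schedule), so L = 8.02 to 31.98 h.
- Days 2, 3, 4 and 7: 24 h each, ending at 0800 (collection schedule).
- Treatment window: 54 h after randomization (Section 8, usual temperature management arm).
- Cooling: target expected within 4 h (Section 1.2), held for 48 h, rewarmed to 36 °C at 0.3 °C/h (Section 8).

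**Times after randomization**

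| Point | Formula | Randomized at 2359 | Randomized at 0001 |
|---|---|---|---|
| Day 4 0800 (prompts stop) | L + 72 | 80 h | 104 h |
| Day 6 0800 (prompts resume) | L + 120 | 128 h | 152 h |
| Day 7 0800 | L + 144 | 152 h | 176 h |

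**Gap.** (L + 120) − (L + 72) = 48 h, whatever the clock time of randomization.

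**Share of randomization to Day 7 0800.** 48/176 = 27%; 48/152 = 32%. Prompted coverage is therefore 104/152 = 68% to 128/176 = 73%.

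**Share of the time after the 54 h window.** 176 − 54 = 122 h and 152 − 54 = 98 h. 48/122 = 39%; 48/98 = 49%.

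**Position relative to rewarming.** The gap opens 80 − 54 = 26 h to 104 − 54 = 50 h after the treatment window. Building up from the cooling steps, rewarming from 34 °C takes (36 − 34)/0.3 = 6.7 h, so it ends at about 4 + 48 + 6.7 = 58.7 h, still before the earliest gap start of 80 h.

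**Position relative to the three-day SAE window.** Seventy-two hours after randomization falls 8 to 32 h before the gap. If study days are counted to 0800 instead, Day 3 ends at L + 48, or 56 to 80 h, which is 24 h before the gap.

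**Illustration on assumed rates.** The documents give no event rates. If each patient had a constant risk p per 24 h, the risk over the gap would be 1 − (1 − p)². For p = 1%, 2% and 5% this is 2.0%, 4.0% and 9.8%, or 0.4, 0.8 and 2.0 of 20 patients. This counts events that happen in the gap, not events lost, and assumes that all 20 remain under observation.

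**The case against.** The best defence is that the checkboxes are not the safety system. Staff must record every AE, the AE CRF has no time limit, and patients are seen daily. Section 2.2.1.1.1 makes clinically important unexpected events reportable through the first study week, which includes the gap. A significant bleed on Day 5 is within those duties. This stands: what is missing is an event-specific prompt, not all capture.

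It does not make the AE CRF equivalent. That form relies on someone deciding to make a free-text entry, in a trial that cannot be blinded (Section 1.1). Section 12 tells staff not to report certain organ failures related to ARDS or underlying disease unless considered study-related, and Section 2.2.1.1.1 limits reportable AEs to those not expected in ARDS. New pneumonia leaves room for that judgement; a yes/no box does not. The Section 6 schedule also has no column for Days 5 and 6.

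A second defence is consistency. The form, its instruction and the collection schedule all say 24 h, and several other Day 7 lines (11, 14, 16, 17, 18, 21 and 22) use 24 h. Line 15 is an imperfect precedent, because its Section 10.7 instruction says 24 h while the form says 72 h. That too is fair: line 13 is a design choice that leaves a hole, not a contradiction.

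Three stronger readings are tempting and not supported:
- *Aim 1 safety is under-counted.* Neither document says that the checkboxes feed the SAE comparison, and under the three-day definition in Section 2.2.1.1.1 that comparison ends before the gap. Section 12 sets no time limit on seriousness and Section 2.2.3.2 adds unexpected SAEs in the first week, so late SAEs could be exposed under those readings, but that is a possibility only.
- *The gap biases towards no difference.* The same form serves both arms. Masking a difference would need an excess in the cooled arm that falls in these 48 h and is also missed by the AE CRF.
- *The gap is more than half of the time after rewarming.* On the protocol's 54 h window it is 39-49%. With the 58.7 h estimate it is 48/(176 − 58.7) = 41% to 48/(152 − 58.7) = 51%, so it barely passes half at one extreme.

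**Conclusion.** The concern holds as a gap in systematic capture. No event-specific prompt covers the 48 h from Day 4 0800 to Day 6 0800, which is 27-32% of the time to Day 7 0800 and lies after rewarming. Events there reach the record only through the general AE CRF, so a table built from the daily checkboxes would miss them, and first-week safety may be under-counted. How many events this concerns cannot be derived from the documents.

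The conclusion assumes that sites answer line 13 as written and that the patient is alive and under observation through Day 6. It is a worthwhile improvement to a small safety pilot, not evidence that the SAE comparison is wrong.

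**What to change.** 1. Change line 13 of the Day 7 form, and its instruction in Section 10.7, to a 72 h look-back worded as the time since the Day 4 form. This matches form lines 9, 15 and 19.
2. Exempt line 13 from the 24 h statement in the collection schedule, so that the documents agree.
3. Add to the SAP a descriptive by-arm table of the three prompted events over days 1-7, cross-checked against the AE CRF, with the source stated for each count.

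Prompted coverage to Day 7 0800 rises from 68-73% to 100%. The cost is one form line, one instruction, one schedule note and a slightly longer chart look-back on Day 7. No visit, test or sample is added.

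A lesser alternative is to name the AE CRF as the sole source for the safety tables. That settles which data are used but leaves the window unprompted. Separately, the SAE time windows in Sections 2.2.1.1.1, 2.2.3.2 and 12 should be reconciled, because they decide whether late events count in the SAP's comparison.
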